#### **4.2.3. Analysis Methods**

Unless otherwise stated, the primary analysis of categorical efficacy and health outcomes variables for Phase 2 and Phase 3 portions uses a logistic regression analysis with geographic region, duration of current episode at Baseline (<4 years vs.  $\geq 4$  years), baseline value, and treatment group in the model, except for outcomes related to SF-36 and HADS where the baseline value will not be included. Firth’s correction will be used in order to accommodate

(potential) sparse response data. The p-value and 95% confidence interval (CI) for the odds ratio from the logistic regression model are used for primary statistical inference, unless Firth's correction still results in quasi-separation. In the case, Fisher's exact test will be used for statistical inference. The difference in percentages and 95% CI of the difference in percentages using the Newcombe-Wilson method without continuity correction are used for descriptive purposes, unless otherwise specified. The relative risk and associated 95% CI using the normal approximation method may also be presented. Missing data will generally be imputed using NRI, as described in Section 4.4.1.

The primary analyses for the continuous efficacy and health outcome variables for Phase 2, Week 36 interim analysis and Phase 3 portion uses ANCOVA with geographic region, duration of current episode at Baseline ( $<4$  years vs  $\geq 4$  years), treatment group, and baseline value in the model unless otherwise stated. Type III tests for least-squares (LS) means will be used for statistical comparison between treatment groups. The LS mean difference, standard error, p-value, and 95% CI will also be reported. The method used to handle missing data will be modified last observation carried forward (mLOCF), which will use the most recent non-missing post-baseline assessment. The specific modification to the LOCF is data after an intercurrent event will not be carried forward to replace the missing data. Additional details of the intercurrent event and mLOCF method are described in Section 4.4 and Section 4.4.2.

The primary analysis for treatment comparisons of continuous efficacy variables at the Phase 2 Decision Point interim database lock uses a restricted maximum likelihood-based mixed model for repeated measures (MMRM) analysis. The model will include geographic region, duration of current episode at Baseline ( $<4$  years vs.  $\geq 4$  years), treatment group, visit, treatment-by-visit interaction as fixed categorical effects, and baseline value/baseline value-by-visit interaction as fixed continuous effects, unless otherwise stated. An unstructured covariance structure will be used to model the between- and within-patient errors. If this analysis fails to converge, the heterogeneous autoregressive [ARH(1)], followed by the heterogeneous compound symmetry (CSH), followed by heterogeneous Toeplitz (TOEPH) will be used. The Kenward-Roger method will be used to estimate the denominator degrees of freedom. Type III tests for the LS means will be used for the statistical comparisons. The LS mean difference, standard error, p-value, and CIs will also be reported. Contrasts will be set up within the model to test treatment groups at specific time points of interest. Additional details of the MMRM method are described in Section 4.4.3.

Time-to-event analysis will be performed and analyzed using log-rank test. Kaplan–Meier curves will also be produced. A Cox proportional hazards model may be used with treatment and other stratification variables in the model unless, otherwise, stated. Hazard ratio with CIs may be reported. Diagnostic tests for checking the validity of the proportional hazards assumption may be performed. If the assumption of proportional hazards is not justified, nonproportionality may be modeled by stratification.

Note that for analysis conducted on the randomized withdrawal population or retreated population, the geographic region and duration of current episode at Baseline may not be used as covariates in the statistical analysis models.

Fisher's exact test will be used to test for differences between baricitinib and placebo group for AEs, discontinuations, and other categorical safety data. Continuous vital signs, body weight, and other continuous safety variables, including laboratory variables, will be analyzed using an ANCOVA with treatment and baseline value in the model. The significance of within-treatment group changes from baseline will be evaluated by testing whether or not the treatment group LSM changes from baseline are different from zero; the standard error for the LSM change will also be displayed. Differences in LSM will be displayed, with the p-value associated with the LSM comparison to placebo or appropriate comparator and a 95% CI on the LSM difference will also be provided. In addition to the LSMs for each group, the within-group p-value for the change from baseline will be displayed.

Due to the COVID-19 pandemic, some visits may have been conducted remotely. In order to evaluate the impact of remote visits on the clinical trial, sites were required to record the visit method (e.g., onsite visit, virtual visit, etc.) for visits beginning 1 March 2020. For data collected at the unscheduled postbaseline visit that falls within the visit window, the visit method should be considered the same as recorded for the scheduled visit for this window. If the visit method is a telephone interview or a virtual visit, the visit is considered remote. However, if the visit method is missing for the scheduled visit, but central lab was collected and/or vital assessments are available, then it will be considered an onsite visit, otherwise it will be considered a remote visit.

For F-DBL the analyses for the efficacy and safety will be only descriptive statistics provided to both categorical and continuous endpoints. No statistical inferential test will be provided, unless stated otherwise.

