**Figure JAHO.3.2. Illustration of study design for Clinical Protocol I4V-MC-JAHO(e).**

### 3.2. Method of Assignment to Treatment

Different randomization schemes will be used at Visit 2: two during Stage 1 and one during Stage 2. In Stage 1, the first approximately 100 patients who meet all criteria for enrollment will be randomized in a 1:1:1:1 ratio to receive placebo QD, baricitinib 1 mg QD, baricitinib 2-mg QD, or baricitinib 4-mg QD double-blind treatment at Visit 2 (Week 0). After that, up to a maximum of approximately 200 additional patients are anticipated to be randomized during Stage 1, prior to the Decision Point, in a 2:2:3 ratio to receive placebo QD, baricitinib 2-mg QD or baricitinib 4-mg QD. At the Decision Point, baricitinib 4-mg and 2-mg were selected to continue into Stage 2. Therefore, after the Decision Point, patients will continue to be randomized in a 2:2:3 ratio to receive placebo QD, baricitinib 2-mg QD, or baricitinib 4-mg QD. Baseline randomization will be stratified by geographic region (North America, Japan for Phase 2 portion, and North America, Asia, and Rest of World for Phase 3 portion), and duration of current episode at Baseline (less than 4 years versus at least 4 years) for the whole study. Randomization for the randomized withdrawal period will not be stratified. Assignment to treatment groups will be determined by a computer-generated random sequence using an IWRS. The IWRS will be used to assign bottles, each containing double-blind IP tablets, to each patient, starting at Visit 2 (Week 0), and at each visit up to and including Visit 23 (Week 184). Site personnel will confirm that they have located the correct bottles by entering a confirmation number found on the bottle into the IWRS.

This study will be conducted internationally in multiple sites. [Table JAH0.3.1](#) describes how regions will be defined for stratification. Regions may be combined for statistical analyses in the case when one of the region strata fails to meet the required minimum number of 30 patients. The 2 region strata with the least number of patients will then be pooled.

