		Logistic Regression using NRI b	FAS	Bari 4-mg dose or Bari 2-mg dose vs PBO at Week 36;	Sensitivity analysis
		Tipping point analysis a with Logistic Regression	FAS	Bari 4-mg dose or Bari 2-mg dose vs PBO at Week 36;	Supplementary analysis
		Logistic Regression using NRI a	FAS	Bari 4-mg dose or Bari 2-mg dose vs PBO at Weeks 16, 24;	Key secondary analysis
		Logistic Regression using NRI a	mFAS	Bari 4-mg dose or Bari 2-mg dose vs PBO at Weeks 16, 24;	Supplementary analysis
		Logistic Regression using MI a +NRI a	FAS	Bari 4-mg dose or Bari 2-mg dose vs PBO at Weeks 16, 24;	Supplementary analysis
		Logistic Regression using NRI b	FAS	Bari 4-mg dose or Bari 2-mg dose vs PBO at Weeks 16, 24;	Sensitivity analysis
		Logistic Regression using NRI a	FAS (Severe SALT subgroup c ); FAS (Very severe SALT subgroup c )	Bari 4-mg dose or Bari 2-mg dose vs PBO at Week 36;	Dosing evaluation analysis
		Logistic Regression using NRI a	FAS (Duration of current AA episode < 4 years subgroup d ); FAS (Duration of current AA episode $\geq$ 4 years subgroup d )	Bari 4-mg dose or Bari 2-mg dose vs PBO at Week 36;	Dosing evaluation analysis

Measure	Variable	Analysis Method (Section 4.2.3)	Population (Section 4.2.1)	Comparison/Time Point	Analysis Type
	Proportion of patients achieving SALT 100	Logistic Regression using NRI a	FAS	Bari 4-mg dose or Bari 2-mg dose vs PBO at Weeks 24 and 36;	Other secondary analysis
	Time to achieve SALT $\leq$ 20	Time-to-event analysis a	FAS	Bari 4-mg dose or Bari 2-mg dose vs PBO up to Week 36;	Other secondary analysis
	Proportion of patients achieving an absolute SALT $\leq$ 10	Logistic Regression using NRI a	FAS	Bari 4-mg dose or Bari 2-mg dose vs PBO at Weeks 24 and 36;	Key secondary analysis
		Logistic Regression using NRI a	mFAS	Bari 4-mg dose or Bari 2-mg dose vs PBO at Weeks 24 and 36;	Supplementary analysis
		Logistic Regression using MI a +NRI a	FAS	Bari 4-mg dose or Bari 2-mg dose vs PBO at Weeks 24 and 36;	Supplementary analysis
		Logistic Regression using NRI b	FAS	Bari 4-mg dose or Bari 2-mg dose vs PBO at Weeks 24 and 36;	Sensitivity analysis

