#### **4.11.1. Primary Outcome and Methodology**

The primary analysis of the Phase 3 portion of this study is to test the hypothesis that the 4-mg dose or 2-mg dose of baricitinib is superior to placebo in the treatment of patients with severe or very severe Alopecia Areata (AA), as assessed by the proportion of patients achieving SALT $\leq$  20 at Week 36 using the FAS population, assuming that treatment response disappears at the visits conducted remotely due to COVID-19 or after the patient discontinued study or study treatment. This will serve as the primary estimand. In this estimand, missing data due to the application of the primary censoring rule and the occurrence of other non-censor intercurrent events will be imputed using the NRI method described in Section 4.4.1.

A logistic regression analysis as described in Section 4.2.3 will be used for the comparisons. The odds ratio, the corresponding 95% CIs and p-value, as well as the treatment differences and the corresponding 95% CIs, will be reported. In the case when Firth's correction still results in quasi-separation, Fisher's exact test will be used for primary analysis.

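### The only committed test for time to SALT ≤20 is an unstratified log-rank test, although Phase 3 randomisation is stratified by region and episode duration; the effect is conservative and usually small, and the repair is nearly free.

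*SAP*

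**What the plan says.** SAP Section 3.2 names two stratification factors: "Baseline randomization will be stratified by geographic region" (North America, Asia and Rest of World in Phase 3) and "duration of current episode at Baseline (less than 4 years versus at least 4 years) for the whole study". That makes six strata. Section 3.2 also lets the two smallest regions be pooled when a region has fewer than 30 patients.

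Section 4.3 makes adjustment for both factors the default for statistical models, and Section 4.2.3 names both in the logistic, ANCOVA and MMRM analyses.

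For time-to-event outcomes, Section 4.2.3 says "Time-to-event analysis will be performed and analyzed using log-rank test" and then "A Cox proportional hazards model may be used with treatment and other stratification variables in the model". Reporting a hazard ratio is likewise optional. Table JAHO.4.7 applies the time-to-event analysis to time to SALT ≤20 in the FAS as "Bari 4-mg dose or Bari 2-mg dose vs PBO up to Week 36". Table JAHO.2.1 lists the endpoint under other secondary objectives, which are not multiplicity-adjusted.

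For the primary endpoint, Section 4.2.3 says "The p-value and 95% confidence interval (CI) for the odds ratio from the logistic regression model are used for primary statistical inference", from a model that contains region, duration and the baseline value.

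**The concern.** A log-rank test takes no covariates, so the default in Section 4.3, which speaks of models, does not clearly reach it. Section 4.2.3 relaxes the two covariates only for the randomised withdrawal and retreated populations. Nothing exempts this FAS comparison.

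Stratified randomisation removes chance imbalance between arms on the stratification factors. An unstratified test still counts between-stratum variation as noise. If the factors predict response, its variance is too large, its true size falls below nominal and some power is lost.

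There is also a small pre-specification gap. The endpoint has a committed unadjusted test and an optional adjusted model, with no rule for when the second is run or reported. A hazard ratio from the adjusted model would then not correspond to the p-value from the test.

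**Working it through.** **The plan's own power figure.** Inputs from SAP Section 4.1: about 625 Phase 3 patients, 2:2:3 allocation, response of 5% (placebo), 20% (2-mg) and 30% (4-mg), and two-sided Fisher exact tests at 0.01 (2-mg) and 0.04 (4-mg).

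- Arm sizes: 625 × 2/7 ≈ 179 for placebo and for 2-mg; 625 − 179 − 179 = 267 for 4-mg.
- Exact enumeration gives power of 96.1% for 2-mg and above 99.99% for 4-mg. The stated figure of more than 90% is reproduced.

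**Assumptions.** The documents give neither the mix nor the prognostic strength of the strata. Assumed here: region shares 50/30/20%, duration shares 60/40%, responses first seen at Weeks 12 to 36. The odds ratios for duration and for the extreme regions run from 1/1 (none) through 2/1.5 and 3/2 (moderate) to 5/3 (strong).

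**Size of the unstratified test.** With arms balanced within strata, the ratio of actual to assumed null variance is approximately

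R = Σ w_s p_s(1 − p_s) / [p(1 − p)],

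where w_s is the stratum share, p_s the stratum response rate and p the overall rate. The true size is 2[1 − Φ(1.96/√R)], and the excess in the standard error is 1/√R − 1.

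Worked case, odds ratios 3/2 at 20% overall response:

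- Shares 0.30, 0.20, 0.18, 0.12, 0.12, 0.08, with stratum rates 0.215, 0.084, 0.279, 0.114, 0.354, 0.154.
- Σ w_s p_s(1 − p_s) = 0.1522 and p(1 − p) = 0.16, so R = 0.951.
- 1.96/√0.951 = 2.01, so the size is 4.45% and the standard error is 2.5% too large.

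Power comes from simulation of 179 versus 179 patients at 5% versus 12%, balanced within six strata, 3000 replicates:

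| Odds ratios (duration / region) | True size at 5%, 20%, 30% response | Standard error excess | Power, unstratified vs stratified |
|---|---|---|---|
| 1 / 1 | 5.0, 5.0, 5.0% | 0% | 66.4 vs 66.0% |
| 2 / 1.5 | 4.9, 4.8, 4.7% | 0.3–1.4% | 66.3 vs 66.8% |
| 3 / 2 | 4.8, 4.5, 4.3% | 0.7–3.4% | 66.3 vs 67.4% |
| 5 / 3 | 4.7, 3.9, 3.6% | 1.5–7.1% | 69.5 vs 70.7% |

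Simulation error is about 0.9 points on power. At the planned 5% versus 30%, both tests rejected in every one of 1500 replicates. At 5% versus 20%, both exceed 99%.

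**Larger losses.** These need strong strata together with response rates away from the planning values. With assumed hazard ratios of 4 for duration and 2 between extreme regions, power was 60% versus 64% at 20% versus 12%, and 63% versus 71% at 40% versus 28%. Null rejection was 3.4% unstratified and 5.0% stratified.

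**Descriptive risk difference.** At 5% versus 30%, the Newcombe-Wilson interval is 0.129 wide. A Mantel-Haenszel stratified interval is 0.127 wide with no stratum effect and 0.124 with the strongest. Stratification itself therefore accounts for at most 0.003, or 0.003/0.127 ≈ 2%. The rest is the difference between interval methods.

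**The case against.** **Stronger reading.** A reader might infer that the primary result is also mis-specified, because Section 4.11.1 (Primary Outcome and Methodology) says "The odds ratio, the corresponding 95% CIs and p-value, as well as the treatment differences and the corresponding 95% CIs, will be reported" and the difference has an interval with no strata. The documents do not support that. The primary p-value comes from a model with both factors; only the Fisher fallback, used if quasi-separation persists, is unadjusted. Of the difference itself, Section 4.2.3 says: "The difference in percentages and 95% CI of the difference in percentages using the Newcombe-Wilson method without continuity correction are used for descriptive purposes". It has no p-value of its own, and a crude interval beside crude percentages is a coherent summary.

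**Weight.** The endpoint is outside the controlled family, no other test depends on it, and any error is on the safe side. The loss is zero if the strata are not prognostic. All of this stands and limits the importance of the point.

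**Adjustment is already available.** The Cox model can include the factors. But it is optional, so the committed analysis remains the unstratified test.

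**Timing.** SAP Version 4 preceded the Week 36 lock and Version 5 serves the final lock, where Section 4.2.3 makes the analyses descriptive unless stated otherwise. The addendum's rationale reports the Week 36 efficacy result as known. A stratified test run now cannot be presented as the prespecified one. This stands.

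**Sparsity.** At 5% response, 179 placebo patients give 179 × 0.05 ≈ 9 responders over six strata. That calls for a pooling rule; it is not a reason to leave the strata out.

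**Conclusion.** The point holds as a low-cost improvement to one uncontrolled secondary analysis. As written, the log-rank test for time to SALT ≤20 uses neither randomisation factor, unlike the SAP's logistic, ANCOVA and MMRM analyses.

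The consequence is conditional: no effect if the factors are not prognostic, a true size of about 4.3 to 4.9% under moderate assumed effects, and about 3.6% under strong ones. Power loss is usually about 1 point or less, and reaches several points only with strong strata and response rates away from the planning values. Every one of these magnitudes rests on assumed stratum shares and effects. To call the test too conservative without that condition would go beyond what the documents show.

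**What to change.** In SAP Section 4.2.3, specify for the FAS a *log-rank test stratified by geographic region and duration of current episode (<4 vs ≥4 years)*, with sparse regions pooled as in Section 3.2. Make the Cox model with the same two factors definite, so that the hazard ratio matches the test. If this is run after the Week 36 lock, label it supplementary and keep the unstratified result as the prespecified one.

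Optionally, show a Mantel-Haenszel stratified Newcombe interval, or a standardised risk difference from the fitted logistic model, beside the crude descriptive interval and not in place of it.

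The cost is a line or two of SAP text and a strata option in the program; no new data are needed. Strata without events, or with patients in only one arm, add nothing to the stratified test. An adjusted difference may not equal the subtraction of the crude percentages, which needs a table footnote.

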#### **4.2.2. Definition of Baseline and Postbaseline Measures**

The baseline utilized in the efficacy analyses depends on the analysis being performed. The baseline value for the efficacy and health outcome analyses for all populations is defined as the last non-missing measurement on or prior to the date of first study drug administration (expected at Week 0, Visit 2) unless otherwise stated. If a patient is randomized but does not receive study drug, then the date of randomization is used instead of the first dose date. The efficacy and health outcome analyses for the randomized withdrawal population will use the measurement on or immediate prior to the date of Visit 2 (Week 0) or date of visit 11 (Week 52) as baseline as appropriate for the endpoints, unless otherwise stated. The efficacy and health outcome analyses for the retreated population will use the measurement on or prior to the date when patients got retreated.

Baseline for the safety analyses is defined as the last non-missing scheduled (planned) measurement on or prior to the date of first study drug administration for continuous measures by-visit analyses, unless otherwise stated, and all non-missing measurements on or prior to the date of first study drug administration for all other analyses.

Postbaseline measurements are collected after study drug administration through Week 200 (Visit 24) or early discontinuation visit. For data collected in the electronic Clinical Outcomes Assessment (eCOA) tablet (including Patient-Reported Outcomes [PRO] and Clinician-Reported Outcomes [ClinRO]) and related to efficacy assessments, unscheduled postbaseline visits that fall within the visit windows defined by Lilly will be summarized in the by-visit analyses if there is no scheduled visit available. Refer to clinical protocol I4V-MC-JAHO(e) for detail of the visit windows. If there is more than 1 unscheduled visit within the defined visit window and no scheduled visit is available, the unscheduled visit closest to the scheduled visit date will be used. If 2 unscheduled visits of equal distance are available, then the latter of the 2 will be used.

Postbaseline measures for the safety analyses are defined as the non-missing scheduled (planned) measurements after the date of first study drug administration for continuous measures by-visit analyses and all non-missing measurements after the date of first study drug administration for all other analyses.

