### 4.4. Handling of Dropouts or Missing Data

Depending on the estimand being addressed, different methods will be used to handle missing data as a result of intercurrent events. Intercurrent events can occur through but not limited to the following:

- application of one of the censoring rules (including after permanent study drug discontinuation, after rescue therapy, after dose change, or retreatment)
- discontinuation of inadvertently enrolled patients
- discontinuation from the study due to enrollment in other trials, medical, safety or regulatory reasons, investigator decision, and patient decision
- missing an intermediate visit prior to discontinuation, rescue, dose change, or retreatment
- loss to follow-up.

Non-censor intercurrent events are events that are not due to the application of any censoring rule, i.e., the last four items in the list above.

Note that as efficacy and health outcome data can accrue after a patient permanently discontinues study drug or begins rescue therapy or retreatment, specific censoring rules to the data will be applied to all efficacy and health outcome observations subsequent to these events depending on the estimand being addressed. These specific censoring rules are described below.

*The primary censoring rule* will censor efficacy and health outcome results after permanent study drug discontinuation or results that were collected during remote visits due to the COVID-19 pandemic. Therefore, the data collected remotely will be considered “missing”. This censoring rule will generally be applied to all efficacy and health outcome endpoints and conducted for all defined efficacy analysis populations in the Phase 3 portion except for the Randomized Withdrawal Population (defined in Section 4.2.1).

*A secondary censoring rule* will censor efficacy and health outcome results after permanent study drug discontinuation. This censoring rule will not exclude the data collected during remote visits due to the COVID-19 pandemic and will be applied to selected efficacy and health outcome endpoints conducted for the FAS population (defined in Section 4.2.1). This censoring rule will be applied to uptitration population.

*A tertiary censoring rule* will censor efficacy and health outcome results after permanent study drug discontinuation or after retreatment. This censoring rule will be applied to the Randomized Withdrawal Population (defined in Section 4.2.1).

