#### **4.4.1. Nonresponder Imputation**

For the analysis of categorical efficacy and health outcomes variables such as SALT  $\leq$  20 and PRO for Scalp Hair Assessment score of 0 or 1 with a  $\geq$ 2-point improvement from Baseline, the primary imputation method when an intercurrent event occurs will be nonresponder imputation (NRI), which can be justified based on the composite strategy ([ICH 2019]) for handling intercurrent events. This imputation procedure assumes that the effects of treatments disappear

after the occurrence of the intercurrent event. For analyses that utilize any of the censoring methods, randomized patients without at least 1 post-baseline observation will also be defined as nonresponders for all visits. As well, patients who are missing a value prior to discontinuation, rescue, dose change, or retreatment (if censoring on rescue or retreatment), i.e., the patient is missing an intermediate visit, will be imputed as nonresponders on that visit only.

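### SAP 4.2.3 labels an in-window unscheduled efficacy value by the scheduled visit's method, so an on-site make-up SALT can be censored as remote

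*SAP*

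**What the plan says.** Four parts of the SAP act in sequence.

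- **Selection (4.2.2).** For efficacy data from the eCOA tablet, an unscheduled value inside the window "will be summarized in the by-visit analyses if there is no scheduled visit available".
- **Label (4.2.3).** For such data, "the visit method should be considered the same as recorded for the scheduled visit for this window". The definition of remote is: "If the visit method is a telephone interview or a virtual visit, the visit is considered remote". A fallback treats the visit as on site "if the visit method is missing for the scheduled visit, but central lab was collected and/or vital assessments are available". It applies only when the scheduled visit's method is missing, so it cannot help once a telephone or virtual visit has been recorded.
- **Censoring (4.4).** The primary rule censors "results that were collected during remote visits due to the COVID-19 pandemic" and sets them to missing. The tertiary plus rule also removes remote results.
- **Imputation (4.4.1, 4.11.1).** For the primary endpoint, "missing data due to the application of the primary censoring rule and the occurrence of other non-censor intercurrent events will be imputed using the NRI". A patient without a value before discontinuation, "i.e., the patient is missing an intermediate visit, will be imputed as nonresponders on that visit only". For continuous SALT endpoints, 4.2.3 and 4.4.2 use mLOCF instead.

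The primary estimand (2.1, 4.11.1) takes response to be lost at visits that were conducted remotely.

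**The concern.** The estimand and the censoring rule both turn on how a result was obtained. The labelling rule in 4.2.3 substitutes the method of a different visit.

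The case where this matters is foreseeable. SAP 4.4.4 acknowledges that some efficacy assessments are not collected at remote visits, and that is when an on-site make-up assessment would be wanted. If it falls inside the window, it is the only SALT available, and the rule labels it remote.

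For the endpoints analysed with NRI, an observed on-site result then becomes a failure whatever its value. Only responders are changed by this, so the arm with more responders loses more of them and the treatment difference shrinks. For percent change in SALT, the on-site value gives way to an earlier one.

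The opposite error is possible but narrower. A virtual unscheduled SALT passes as on site only if the scheduled visit was on site and yielded no SALT.

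**Working it through.** **1. Tracing one patient through the rules**

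The Week 36 visit is by telephone, and a clinic SALT is obtained later inside the window.

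| Situation | 4.2.2 selects | Label | Primary analysis, SALT ≤20 |
|---|---|---|---|
| No SALT at the remote visit | on-site unscheduled value | remote, inherited under 4.2.3 | censored, then nonresponse |
| SALT recorded at a virtual visit | scheduled value | remote, correctly | censored, then nonresponse |

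In the first row the label is the cause. In the second the order of precedence in 4.2.2 is the cause. Both lose the on-site value, so correcting 4.2.3 alone leaves the second case open.

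**2. The SAP's own power figure**

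Inputs from SAP 3.1.1 and 4.1: about 625 Phase 3 patients at 2:2:3; response 30% (4-mg), 20% (2-mg) and 5% (placebo); two-sided Fisher exact test at 0.04 (4-mg) and 0.01 (2-mg); stated power above 90%.

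- 4-mg: 625 × 3/7 ≈ 268
- 2-mg and placebo: 625 × 2/7 ≈ 179 each

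Exact Fisher power by full enumeration is above 99.9% for 4-mg and 96.05% for 2-mg. The stated figure is reproduced.

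**3. Size of the effect**

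Let f be the share of patients whose on-site Week 36 SALT is lost to the rule. The documents give no value, so f is an assumption, taken as equal across arms and unrelated to response. Each rate becomes p(1 − f), so each difference is multiplied by (1 − f).

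| f | 4-mg difference, 25.0(1 − f) | 2-mg difference, 15.0(1 − f) | 2-mg power, alpha 0.01 |
|---|---|---|---|
| 0 | 25.0 | 15.0 | 96.05% |
| 1% | 24.75 | 14.85 | 95.83% |
| 2% | 24.5 | 14.7 | 95.59% |
| 5% | 23.75 | 14.25 | 94.81% |
| 10% | 22.5 | 13.5 | 93.25% |
| 20% | 20.0 | 12.0 | 88.85% |

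The 4-mg power stays above 99.9% throughout. SAP 4.6 gives each dose an initial 0.025; at that level 2-mg power is 98.3% at f = 0, 97.64% at 5% and 94.03% at 20%.

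Responders turned into failures, as n × f × p:

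- 4-mg: 268 × 0.01 × 0.30 = 0.8, up to 268 × 0.05 × 0.30 = 4.0
- placebo: 179 × 0.01 × 0.05 = 0.09, up to 179 × 0.05 × 0.05 = 0.45

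**4. Whether a planned analysis isolates the error**

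- The NRI sensitivity analysis under the secondary censoring rule (Table JAHO.4.7) keeps the mislabelled value. It also admits every truly remote value, so the two effects are mixed.
- The MI plus NRI hybrid (4.4.4) does not impute failure here, but it still discards the observed value and replaces it with imputed draws.

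**The case against.** **The SAP already examines this.** Two planned analyses avoid counting the patient as a failure. A reader might infer that the value is thrown away in every analysis, and that is not so. What remains is that neither analysis answers the narrow question of the result with correct labels.

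**Read literally, 4.2.2 excludes the value first.** A telephone visit did take place, so a scheduled visit was arguably available and 4.2.3 never comes into play. But the sentence in 4.2.3 presupposes usable unscheduled data in a window whose scheduled visit has a recorded method; on the literal reading it would have almost nothing to govern. The on-site value would be lost on that reading too.

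**Inheritance is sometimes right.** A tablet entry filed as unscheduled but made at the scheduled visit should take that visit's method. This stands, although the SAP does not limit the rule to such records.

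**The choice is conservative.** It shrinks the difference and does not favour baricitinib. This also stands, but the estimand is defined by remote conduct, and an on-site assessment does not meet that definition.

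**The reach is limited.** A reader might infer that every analysis depending on the remote flag turns the value into failure. Percent change in SALT uses mLOCF, and the tertiary plus analyses include MI plus NRI, MI plus mLOCF and mLOCF alone. Final-lock SALT analyses use secondary or tertiary censoring, which retains remote data. The addendum uses observed cases without imputation and, even in exceptional circumstances, requires a live Week 52 visit. None of these final-lock SALT or addendum analyses is affected.

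**Conclusion.** The point holds in a limited form. Followed as written, SAP 4.2.3 gives an on-site unscheduled value a remote label whenever the scheduled visit in that window was recorded as remote. Under the primary rule this means nonresponse for SALT ≤20 and the binary key secondaries, and an earlier value for continuous SALT.

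The effect is probably small. At an assumed 1-5%, the 4-mg difference falls by 0.25-1.25 points and 2-mg power by about 0.2-1.2 points. Power at the SAP's planning levels stays above 90% up to f = 10%. A reader might infer that the primary result is in doubt; the figures do not support that.

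The size rests on an assumed frequency, equal across arms and independent of response, and on the SAP's planning rates. The main study's visit windows and remote-visit rules are in the JAHO(e) protocol, which is not among these documents, so the frequency cannot be narrowed further.

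**What to change.** - **SAP 4.2.3.** Classify each efficacy value by the method of the visit at which it was collected. Inherit the scheduled visit's method only for records dated the same day as that visit. Otherwise use the unscheduled visit's own recorded method or, if there is none, the existing laboratory and vital-signs fallback applied to that date.
- **SAP 4.2.2.** Under rules that censor remote data, let an in-window on-site unscheduled value replace a remote scheduled one. Other rules need no change.
- **Remaining analyses.** Apply this to the tertiary plus analyses still to be run, for example Skindex-16, HADS and EQ-5D-5L in Table JAHO.4.19.
- **Week 36 endpoints.** The remote-visit definition entered in SAP Version 4, approved before the Week 36 lock, and Version 5 serves the final lock. Rewording now does not alter the prespecified primary analysis. Count the affected records by arm and report a re-derived result as a sensitivity analysis.

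The cost is two wording changes, one derivation and one tabulation. The SAP requires sites to record visit method from 1 March 2020 but does not say that unscheduled visits carry their own. An on-site make-up visit with no recorded method, laboratory sample or vital signs would still default to remote, so some affected values may not be recovered.
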